6.3 Treatment Assignment Procedures

6.3.1 Randomization Procedures

Participants will be randomized using a pre-prepared block randomization schedule, linked to study enrolment number.

Ninety-nine (99) infant participants will be recruited, randomized and allocated into 3 groups: BCG (single dose level 2.5 x 10^5 CFU/0.05 mL, n=24); or MTBVAC at three different dose levels as a single intradermal dose of 2.5 x 10^4 CFU (Cohort 1, n=25), 2.5 x 10^5 CFU (Cohort 2, n=25), and either 2.5 x 10^6 CFU (n=25) or 2.5 x 10^5 CFU (n=13) plus 2.5 x 10^4 CFU (n=12) (Cohort 3) (24 BCG; 75 MTBVAC).

Vaccination of newborns will be staggered to allow gradual evaluation of safety and reactogenicity at each escalation of MTBVAC dose. Progression from the 2.5×10^5 to the 2.5×10^6 CFU dose level, for which safety has not yet been demonstrated, will require that all of the following criteria have been met: (1) no pre-defined pausing rules have been observed at lower MTBVAC dose levels in this trial; (2) favourable review of day 28 safety data of all lower MTBVAC dose groups by the Data Safety Monitoring Board (DSMB); (3) favourable review of safety data from the current pilot Phase 1b infant trial by the DSMB; and (4) favourable review of day 28 safety data for the 2.5×10^6 CFU dose level in QFT negative adults in the parallel adult trial by the DSMB. In the event that any one of these safety criteria are not met, Cohorts 1 and 2 will be expanded so that 33 additional neonates will randomly allocated to receive the 2.5×10^4 CFU dose (n=12), the 2.5×10^5 CFU dose (n=13) or BCG (n=8) by default. If there is a delay in adult data, dose escalation in infants will either be delayed, or Cohorts 1 and 2 be expanded as mentioned above.

6.3.2 Masking Procedures

MTBVAC and BCG vaccine will be prepared, and allocation concealed by the site pharmacist. All other site staff will be blinded to vaccine allocation, throughout the follow-up period. Individually-sealed code break envelopes will be held by the pharmacist in case emergency unblinding is necessary.

Data pertaining to the MTBVAC vaccine and to BCG control will be collected in an observer-blinded manner. By observer blinded, we mean that during the course of the study the vaccine recipient and those responsible for the evaluation of safety and reactogenicity study parameters, will all be unaware of which vaccine preparation was administered to a particular participant. To do so, the MTBVAC vaccine and BCG control will be prepared and blinded by the pharmacist, whereas, the vaccination will be administered by the Vaccination Nurse, a research nurse not involved in follow up and safety evaluations of participants. The principal investigator and the sub-investigators will be responsible for assessing safety and reactogenicity. Blinding will be maintained throughout the vaccination and follow-up portions of the vaccine trial. It is not yet known whether MTBVAC offers equivalent or better protection against TB compared to BCG. Therefore, measures to minimize risk of TB will be put in place

throughout the study and, after completion of all Study D365 visits in each cohort and unblinding of the clinical team, 'catch up' BCG vaccination will be given to all MTBVAC vaccinated infants once the last participant of each cohort performed the Post D365 visit.

No set of individual codes will be held at Biofabri's Headquarters. Biofabri's Headquarters will be able to access the individual randomization code from the SATVI Pharmacy randomization register. The code will be broken by the SATVI Pharmacist (Study Contact for Emergency Code Break) only in the case of medical events that the investigator/physician in charge of the participant feels cannot be treated without knowing the identity of the study vaccine(s).

Biofabri's policy (incorporating ICH E2A guidance, EU Clinical Trial Directive) is to unblind any serious adverse event (SAE) report associated with the use of the investigational product, which is unexpected and attributable/suspected, prior to regulatory reporting. The SATVI Pharmacist is responsible for unblinding the treatment assignment in accordance with specified time frames for expedited reporting of SAEs (Refer to Section 10.9).

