It is not yet known whether MTBVAC offers equivalent, better, or worse protection against TB compared to BCG. Therefore, measures to minimize risk of TB will be put in place throughout the study and, after completion of all Study D365 visits in each cohort and unblinding of the clinical team, 'catch up' BCG vaccination will be given to all MTBVAC vaccinated infants once the last participant of each cohort has performed the D365 visit, provided that the individual recipients have a negative screen for active TB disease and new household contacts, and do not have a new positive QFT result at D365. Risk of incident TB disease will be minimized by exclusion of infants with known TB exposure, including prior maternal or family history. Newborns born to HIV infected mothers, with increased risk of TB, will not be enrolled. All infants will be screened actively for TB symptoms at each study visit to diagnose TB disease early and pre-empt severe morbidity. Infants diagnosed with TB disease will remain in safety follow-up, but will be referred immediately for TB treatment, provided free of charge by health services. In the previous South African study we saw no confirmed TB cases in either adults or infants who received MTBVAC. One adult MTBVAC recipient with recent HIV seroconversion was diagnosed with aseptic meningitis and received 6 months treatment for unconfirmed TB meningitis. Two infant MTBVAC recipients (one QFT+; one QFT-) received TB treatment in the public health system for unconfirmed TB; a rate (2/28; 7%) that is similar to the rate of unconfirmed TB in a previous infant trial in this community (13% over 2 years)[29]

The QFT assay is widely used in older children and adults as a tool to aid in the diagnosis of *M. tuberculosis* infection. Given the preliminary evidence of MTBVAC vaccine induced QFT conversion in the current Phase 1b infant study, it is postulated that infants who receive MTBVAC will demonstrate QFT conversion events two months after vaccination (D56), followed by a high rate of reversion, leading to declining rates of QFT positivity at D182 and D365. The same response kinetic was observed for BCG-specific T cell responses in a prior longitudinal study in newborns (15). The observed effect of MTBVAC on QFT conversion is analogous to the known effect of BCG on false positive TST conversion; MTBVAC might be expected to have a similar effect on TST conversion.

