8.4 Final Study Visit

Study Day 365

Allowable window for clinic visit is 365 ±14 days from Study Day 0 visit date.

- 1. Verbally reconfirm consent.
- 2. Update medical history including use of medications.
- 3. Screening for potential new TB exposure and TB symptoms.
- 4. Record feeding practice.
- 5. Vital signs (heart rate, respiratory rate, axillary temperature, weight and recumbent length).
- 6. Focused physical examination.
- 7. Record any serious adverse events (including concomitant medications) and unsolicited adverse events.
- 8. Examine site of injection (includes measurement of redness, swelling, and ulceration) and take a pus swab if discharge present.
- 9. Blood collection for:
 - Immunogenicity WB-ICS
 - QuantiFERON®-TB Gold Plus

Post Cohort Unblinding of Participants Post Study Day 365

Participant, and subsequent clinical team unblinding will occur when all infants in a given cohort have attained their Study Day 365 visit.

- MTBVAC recipients who have tested QFT positive will be given a card stating that they
 have received an investigational vaccine that may interfere with interpretation of future
 IGRA and TST tests.
- BCG rescue dose will be offered to all MTBVAC recipients in this cohort, given that the
 individual recipients have a negative screen for active TB disease and new household
 contacts, and do not have a new positive QFT result at D365. Any MTBVAC recipient
 receiving IPT will be offered the BCG rescue dose after completion of IPT.
- 3. The site will contact the participant's caregiver telephonically (or perform a home visit if no telephone available) 14 days post vaccination with the BCG rescue dose to enquire about the infant's wellbeing and BCG injection site reaction, and respond appropriately to any adverse reaction.

Note: The immunology team will remain blinded until immunology database lock.

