8.5 Early Termination Visit

Visit to be conducted if participant discontinues from study prior to Study Day 365.

- 1. Update medical history including use of medications.
- 2. Screening for potential new TB exposure and TB symptoms.
- 3. Record feeding practice.

- 4. Vital signs (heart rate, respiratory rate, axillary temperature, weight and recumbent length).
- 5. Focused physical examination.
- 6. Record any adverse events, including unsolicited adverse events, and serious adverse events (including concomitant medications).
- 7. Examine site of injection (includes measurement of redness, swelling, and ulceration) and take a pus swab if discharge present.
- 8. Blood collection for:
 - QuantiFERON-PLUS TB
 - Confirm contact details for possible BCG rescue dose once all infants in cohort have completed D365 visit.

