9.1.1 Screening for TB and referral for Isoniazid Preventive Therapy

All infants will undergo screening for potential new TB exposure and TB symptoms at each visit and caregivers will be encouraged to report such symptoms or any new household TB contact if they occur in between visits. If TB symptoms or potential new TB exposure are

detected these infants will be investigated for active TB disease and may be referred to the public health clinic for initiation of TB treatment if indicated or IPT if active TB is ruled out.

Early (D56) post-vaccination QFT conversion in infants with low risk of natural *M. tuberculosis* exposure is assumed to be vaccine-induced and will not be treated with isoniazid preventive therapy (IPT). Infants who demonstrate early QFT conversion at D56 will undergo enhanced screening for potential new TB exposure and TB symptoms during all scheduled study visits, and in addition, during interval telephonic contacts at D120 and D270. QFT samples will be collected at D182 and D365 from infants who tested QFT positive at D56, and stored for later analysis, but since a positive QFT result would not be interpretable, these data will not be used for clinical decision-making. All infants who received MTBVAC and tested QFT positive will receive a card at the end of study indicating that they have received an experimental vaccine that may interfere with interpretation of future IGRA and TST tests for TB infection..

QFT assays will be repeated at D182 and D365 in infants who tested QFT negative at D56. These results will be made available for clinical decision-making. Infants with new QFT conversion events at D182 or D365, and any infant with a reported new household TB contact regardless of QFT status, will be referred to the public health services for IPT since these infants would potentially benefit from TB prophylaxis against *M. tuberculosis* infection as per SA national guidelines, provided that signs and symptoms of active TB disease are absent.

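### Section 6.3.2 gives catch-up BCG to all MTBVAC infants without the conditions in 3.3.1 and 8.4, and the QFT condition there does not cover infants who leave early

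*Combined protocol and SAP*

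**What the plan says.** Four sections of the protocol deal with the catch-up (rescue) BCG dose.

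- **6.3.2 Masking Procedures.** The sentence opens with the timing "after completion of all Study D365 visits in each cohort and unblinding of the clinical team" and then says the dose "will be given to all MTBVAC vaccinated infants once the last participant of each cohort performed the Post D365 visit". It states no clinical condition and does not refer to another section.
- **3.3.1 Potential Risks.** The dose is given "once the last participant of each cohort has performed the D365 visit, provided that the individual recipients have a negative screen for active TB". The same screen must also show no new household contact. The QFT proviso is that the infants "do not have a new positive QFT result at D365".
- **8.4 Final Study Visit.** "BCG rescue dose will be offered to all MTBVAC recipients in this cohort, given that the" infants meet the same screen and QFT conditions. A further sentence covers deferral: any MTBVAC recipient "receiving IPT will be offered the BCG rescue dose after completion of IPT".
- **8.5 Early Termination Visit.** A QFT sample is taken, and contact details are confirmed for a "possible BCG rescue dose once all infants in cohort have completed D365 visit".

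On testing, 9.1.1 says that "QFT assays will be repeated at D182 and D365 in infants who tested QFT negative at D56". Sections 3.3.1 and 9.1.1 both refer new converters at D182 or D365, and any infant with a new household TB contact, to public health services for IPT.

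**The concern.** The rule decides which infants receive a live vaccine after the study. Sections 3.3.1 and 8.4 withhold or defer it where TB disease, a new contact or a new infection is possible. Section 6.3.2, read alone, does not. Staff who worked from it would give BCG to infants whom the other two sections exclude or defer.

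The second difficulty lies in the conditions themselves. The QFT condition refers to one visit, D365, which an infant who leaves early never attends. Section 8.5 nevertheless takes a QFT from that infant and keeps the rescue dose open. The result is collected, but no text says how it bears on the dose.

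**Working it through.** No arithmetic applies beyond counting, so the texts are set side by side.

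**Step 1: conditions and trigger by section**

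| Section | TB and contact screen | QFT condition | Deferral for IPT | Trigger |
|---|---|---|---|---|
| 3.3.1 | yes | new positive at D365 | not stated | last D365 visit in cohort |
| 6.3.2 | none | none | none | opens on D365, ends on Post D365 |
| 8.4 | yes | new positive at D365 | yes | all D365 visits in cohort |
| 8.5 | not stated | not stated | not stated | all D365 visits in cohort |

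Three sections give the rule for who receives the dose (3.3.1, 6.3.2, 8.4). Two of them state the conditions and one, 6.3.2, does not. All four rows contain the D365 trigger, and only 6.3.2 adds a second one. Appendix A places the rescue dose in the Post D365 column. Read literally, the end of 6.3.2 makes the dose wait for the visit at which it is given. *Post* is best read as a slip.

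**Step 2: meaning of a new positive.** The protocol does not define it. Sections 3.3.1 and 9.1.1 treat a D56 positive as vaccine-induced and do not use that infant's later QFT results for clinical decisions. Infants negative at D56 are retested, and later conversions are acted on. The reasonable reading is therefore new since a negative D56 test.

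**Step 3: pathways under 3.3.1 and 8.4, on that reading**

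- Positive at D56: the QFT condition does not apply, and the infant stays eligible subject to the screen.
- Negative at D56, positive at D365: blocked, whether or not the infant was already positive at D182.
- Converted at D182 and on IPT: deferred by 8.4.
- Converted at D182, not on IPT, negative at D365: eligible as written (see objection).
- Negative at D56, left before D365, newly positive at the early termination visit: no D365 result exists, so the QFT condition cannot fail. The infant passes it by default.

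**Step 4: could IPT deferral catch the early leaver?** Only if the infant is receiving IPT. The QFT-based referral in 3.3.1 and 9.1.1 names D182 and D365 conversions. A conversion at early termination is not among them, so that result alone does not start IPT. A new household contact would lead to referral regardless of QFT status.

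**Step 5: is there a later check?** In Appendix A the Post D365 column has a TB symptom and contact screen and a physical examination, but no QFT and no blood volume. The scheduled blood volume ends at D365: 2 + 2 + 6 + 8 + 8 = 26 mL.

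**The case against.** The strongest defence is that 6.3.2 is a masking section. Section 8 is where the protocol places its detailed visit procedures, 8.4 states the conditions in full, and 3.3.1 repeats them. Staff would most likely follow 8.4. That stands and limits the practical reach, but it does not remove the contradiction: 6.3.2 is worded as a complete rule.

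For early leavers, 8.5 speaks only of a possible dose, which leaves room for judgement. The screen for active TB and new contacts in 3.3.1 and 8.4 still applies to them. A positive QFT is also not an absolute bar in this protocol, since D56-positive infants stay eligible. These points reduce the risk. They do not say what to do with the QFT result that 8.5 collects.

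A reader might go further and infer that the D365-only condition is wrong for an infant who converted at D182, did not take IPT and is negative again at D365. The documents do not support calling that an error. D365 is the last scheduled QFT before the dose. Reversion is expected for vaccine-induced conversion: in the Phase 1b trial, positivity at the two higher doses fell from 6/8 and 7/9 at day 180 to 2/8 and 4/9 at one year. Section 3.3.1 does regard later conversion as more likely to be natural infection, which is why such infants are referred. But deferring BCG until a course of IPT that is not being taken would have no end point and could leave the infant with neither IPT nor BCG. This is a clinical choice for the sponsor and investigators.

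A reader might also infer that the protocol already refers early-termination converters for IPT. Step 4 shows that it does not.

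**Conclusion.** The point holds as a minor safety-rule inconsistency in two parts. Section 6.3.2 contradicts 3.3.1 and 8.4 by omitting every condition, and it ends on the wrong visit. The QFT condition in 3.3.1 and 8.4 also leaves out an early leaver with a new positive after a negative D56 test, and the IPT referral rule has the same gap.

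The rule covers up to 75 MTBVAC infants. The first part matters only for those with active TB, a new household contact, a new conversion or IPT in progress; the second only for early leavers who have newly converted. The documents give no count for either group, and no dropout rate, rate of conversion after D56 or IPT uptake from which to derive one.

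The conclusion assumes that *new* means new since a negative D56 test. It does not support a claim that infants will in practice be vaccinated against the conditions, because 8.4 states them. Nor does it touch the results: the dose follows the cohort's D365 visits, and no endpoint or analysis depends on it.

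**What to change.** 1. In 6.3.2, replace the catch-up BCG wording with a cross-reference to the conditions in 8.4, and delete *Post*.
2. In 8.4 and the matching proviso in 3.3.1, extend the QFT condition to a new positive at the early termination visit, after a negative D56 test, for infants with no D365 result.
3. Add that early-termination result to the IPT referral rule in 3.3.1 and 9.1.1. Without this, deferral until IPT is complete has no starting point for these infants.

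The treatment of a D182 converter who did not take IPT and is negative at D365 can be left as it is, or settled by the sponsor and investigators as a clinical matter.

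The first change is wording only. The second and third alter eligibility and referral for early leavers. All need a protocol amendment with ethics and regulatory approval (15.1). No visit, test or blood draw is added, because 8.5 already takes the sample. An infant who leaves before D56 has no reference test and is not reached by this change; the TB and contact screen remains the safeguard there.

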
6.3.3 Reasons for Withdrawal

Participants are free to withdraw from participating in the study at any time.

Rules governing the pausing and stopping of investigational product administration between individuals within a single cohort and between cohorts are presented in Section 10.5.

6.3.4 Handling of Withdrawals

Participants who withdraw from participation in the study will be asked to complete a final visit (see Schedule of Events in Appendix A for procedures to be conducted at next visit, which depend on timing of discontinuation from the study). Participants who discontinue the study will not be replaced.

6.3.5 Termination of Study

Rules for pausing or stopping the study are presented in Section 10.5.

7 STUDY INTERVENTION/INVESTIGATIONAL PRODUCT

7.1 Study Product Description

7.1.1 Acquisition

MTBVAC (live attenuated derivative of *Mtb*) was developed at University of Zaragoza, Spain, by [name], and licensed to Biofabri, SL. MTBVAC and excipient solution for dilution will be supplied by Biofabri.

BCG vaccine (BCG SSI, a WHO pre-qualified BCG vaccine)

Formulation, Packaging, and Labeling

The composition of MTBVAC is shown in Table 7-1. Refer to the most recent version of the Vaccine Management Manual for further details on formulation and packaging for MTBVAC.

Table 7-1 Composition of MTBVAC Study Vaccine

Vaccine Dose ^a	Formulation (approximately per standard dose)	Presentation	Volume
MTBVAC 2.5 x 10 ⁵	1.5 – 8.5 x 10⁵ CFU Sucrose Sodium glutamate	Lyophilized pellet in vials (20 doses)	0.05 mL/dose ^b
MTBVAC 2.5 x 10 ⁶	1.5 – 8.5 x 10 ⁶ CFU Sucrose Sodium glutamate	Lyophilized pellet in vials (20 doses)	0.05 mL/dose ^b

a MTBVAC 2.5×10^4 dose to be prepared by dilution with excipient solution of 2.5×10^5 formulation.

Refer to the package insert for formulation details of BCG.

7.1.2 Product Storage and Stability

Upon receipt of investigational product, the study vaccine manager must immediately inspect all vials for damage. Investigational product will be shipped with a continuous temperature-monitoring device. Any damage or discrepancies from the packing list must be documented and promptly discussed with Biofabri and the study monitor to determine the appropriate action.

MTBVAC must be stored at -15 to -30°C in a secured location with no access for unauthorized personnel. MTBVAC excipient solution must be stored at 2-8°C.

BCG must be stored at the manufacturer's recommended temperature range of 2-8°C.

b After reconstitution with 1 mL/vial sterilized water for injection

Refer to the most recent version of the Vaccine Management Manual for detailed instructions regarding investigational product storage.

7.2 Dosage, Preparation and Administration of Study Intervention/Investigational Product

The administered volume is 0.05 mL/dose for all doses of investigational product and BCG. Refer to the most recent version of the Vaccine Management Manual for detailed instructions regarding investigational product preparation. Refer to Section 6.3.2 for masking procedures.

Participants will be administered one dose of the MTBVAC vaccine or BCG active control on Study Day 0. The vaccine dose will be administered intradermally in the deltoid area. Opsite plaster (breathable) will be used to cover the site of injection immediately after vaccination; the plaster will be removed for the 60 minutes post-vaccination injection site examination and then replaced. The participant's caregiver will be provided with additional plasters and will be instructed to change the plaster as needed. Participants will be instructed to protect the plaster and site of vaccination from water. Participants will be provided with a plastic sample bag and clear instructions on how to replace the plaster and will be asked to retain used plasters in the provided plastic bag and return it to clinic for destruction.

Participants will be observed closely for at least 60 minutes following the administration of vaccines, with appropriate medical treatment readily available in case of a rare anaphylactic reaction following the administration of vaccines.

